5.9. Total expected duration of clinical investigation

The dates below are approximate, and no subjects will be enrolled before all required approvals have been obtained. If changes are required, applicable EC and regulatory authorities will be notified.

First subject enrolled: August 15th 2022.

Last subject enrolled: December 1st 2022.

Last subject completed: December 8th 2022.

Final report: June 2023.

6. Clinical Investigation population

The clinical investigation will be conducted with 67 hospitalized subjects enrolled at 3 clinical investigation sites. Each site will enrol about 22-24 subjects at a competitive rate, until the investigation target of 67 subjects is reached.

According to the sample size calculations (see section 10.2) 50 subjects are required to complete the investigation with at least 24 hours of wear time to be counted as completers. Considering a drop-out rate of 30%, the required total number of subjects to be enrolled in the trial shall be 67.

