6.2. Inclusion criteria and Exclusion criteria

Inclusion criteria	Justification for inclusion criteria
Hospital-admitted patients at risk of developing a pressure injury with an expected hospital-stay of more than 24 hours from visit 1	Intended patient population
≥18 years of age and has full legal capacity	To meet the Helsinki declaration
Has given written consent to participate by signing the Informed Consent signature Form	To meet the Helsinki declaration
Has a Braden score of 6-18 at screening (performed within the last 24 hours) (Appendix 2)	To meet primary endpoint
Intact sacral skin (non-breached skin, without signs of non-blanchable erythema over bony prominence/pre-existing sacral pressure injury over bony prominence) (Appendix 3)	Skin must be intact on admission to detect developing pressure injuries during investigation period

Table 2. Inclusion criteria

Exclusion criteria	Justification for exclusion criteria
Suspected or actual spinal injury precluding the patient from being turned	Turning of the patient (to mobilize them) at regular intervals are a part of standard procedure for pressure injury prevention
Sacral erythema, sacral pressure marks, pre-existing sacral pressure injury	Skin must be intact on admission to detect developing pressure injuries during investigation period
Trauma to sacrum	Skin must be intact on admission to detect developing pressure injuries during investigation period.
Topical treatment with steroid creme in the sacral area (treatment must have been terminated at least 14 days prior to enrollment)	Steroid creme may interfere with the skin condition and make it more fragile
Pregnancy or breastfeeding	Even though the ingredients and recipes have been approved for human beings, their effect on embryos, fetuses and infants are unknown

Table 3. Exclusion criteria

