6.4. Recruitment and enrolment

Recruitment of potential subjects will begin once approval have been obtained from the Ethics Committee (EC).

Recruitment will occur through competitive enrolment at 3 different sites in Denmark. The recruitment period from first subject enrolled to last subject enrolled will be approximately 4 months.

Recruitment from hospitals will be via patient screening visits or subject records kept at the participating sites. The Coloplast Clinical Manager will have close contact to each site during the recruitment and enrolment period.

Sites will be instructed to enrol 22-24 eligible hospitalized subjects at a competitive rate. Once the Coloplast Clinical Manager is aware, that 67 subjects have been enrolled, the recruitment will stop.

If, at this time, there are subjects, who have been informed about the investigation (V0) and are reflecting on participation, they will be given the opportunity to be included within the 24 hours post V0.

Recruitment method	Hospital
Potential subjects	Recruitment will go through the Hospital sites. Potential subjects are identified by screening in patient journals using the following searching criteria: 
 • ≥ 18 years of age • Hospital-admitted patients with a limited level of mobility and a Braden score between 6-18 • Expected hospital stay of at least 72 hours
First contact	The potential subjects will be contacted during a planned visit in the ward at the hospital. If a subject is eligible and interested in participating in the investigation upon a short introduction, then written information about the investigation (Informed Consent Form) will be distributed to the subject. The Principal Investigator or delegate will invite the subject to a Screening Visit (V0).
Screening Visit (V0)	At the scheduled Screening Visit (V0) the Principal Investigator or delegate will introduce the investigation and review the inclusion and exclusion criteria. If the subject wishes to reconsider his/her participation at V0, the subject has the right to wait minimum 24 hours before deciding on participation. If the subject hereafter decides to participate in the clinical investigation a Baseline Visit (V1) will be scheduled unless performed the same day as the Screening Visit. If the subject does not meet the inclusion criteria or meet the exclusion criteria, this will be registered at the Subject Pre-Screening Log.

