6.5. Subject withdrawal criteria

The subject can withdraw from the investigation at any time for whatever reason, without any consequences for their future treatment outside the clinical investigation. The Investigator may withdraw a subject from the investigation at any time if they judge it to be the subject's interest.

If dropouts are more than 17 subjects, which entails less than 50 completers, subjects shall be replaced by new subjects.

The investigator must withdraw a subject from the investigation due to:

- Noncompliance with the CIP impacting the scientific integrity of the investigation.
- If subject's safety and wellbeing is compromised by further participation.

- Subjects lost to follow-up. At least three documented attempts will be made to verify subjects lost to follow-up.

Subjects who are prescribed steroid creme for the sacral area, while participating in the investigation, must be withdrawn.

Withdrawn subjects will not be replaced by new subjects. A subject who is withdrawn from the investigation, for any reason, will be encouraged to contact the investigator if problem arises, that the subject believes are related to the clinical investigation. Subject who has not experienced any adverse events, will not be followed up. For subjects who experience adverse events see section 18.1.

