10.1. Statistical design, method and analytical procedures

Definition of analysis populations

Safety populations and Intention to Treat (ITT) will be defined at a formal data review meeting before database lock. As a minimum, the data manager, the clinical manager and the statistician will be involved in the classification of subjects.

The safety population will be constituted by all subjects with valid informed consent. The ITT population (full analysis set) will be constituted by all subjects with valid informed consent, who have been exposed to the Test Product, with information on at least one endpoint.

The summary of the primary and secondary endpoints will be based upon the safety population, whereas the statistical analysis of the exploratory endpoint will be based on the ITT population. Invalid individual data points may be omitted from analysis even though the corresponding subject is part of the ITT population. Any exclusion of data points will be documented.

A formal per protocol (PP) population is not planned due to the explorative nature of the investigation. Considering the data obtained it might be considered to make additional explorative analyses based on a subset of the ITT population.

Analysis of the endpoints and baseline data.

The endpoints as well as baseline assessments will be listed and summarized by descriptive statistics. The summaries will be made for relevant visits (baseline or V1-V8), separately.

Summary statistics for continuous variables are presented with N, Mean, SD (standard deviation), Median, Min and Max, where N denotes the number of subjects contributing with non-missing data. For discrete variables, summary statistics are presented with N and percentage, where percentage is based on the total number of subjects/observations with non-missing data.

The incidence rate (proportion) of hospital-acquired pressure injuries in hospital-admitted patients will be estimated based on the exploratory endpoint (pressure injuries: Yes/No). The proportion of completed subjects answering "Yes" will be calculated. By use of an exact test in the Binomial distribution a 95% confidence interval will be estimated for the proportion.

All statistical analysis will be performed with SAS (version 9.4/Enterprise Guide version 7.1).

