10.2. Sample size

A sample size of 67 subjects will be enrolled with a minimum of 50 completers. This number is assessed to be sufficient to evaluate safety of the product.

The exploratory purpose of the investigation is to estimate the proportion of hospital-acquired pressure injuries in hospital-admitted patients with a 95% confidence interval. The confidence interval is then to be compared with the confidence interval of the results found by Mölnlycke. In the Mölnlycke investigation, the incidence in the control group was estimated to 5.3% [2.3%; 10.1%]³. 50 completing subjects will give a power of more than 80% to show an upper 95% confidence limit of 7.2% or less. This calculation assumes, that the true incidence rate for Biatain Silicone Sacral is 1.2% as we expect it to be as good as the intervention group in the Mölnlycke investigation³. It is further assumed that the confidence interval will be estimated as an exact confidence interval for binomial proportions. The precision of the estimated rate and the chosen sample size is evaluated to be sufficient to draw comparative conclusions between the rate of hospital-acquired sacral pressure injuries found in the suggested observational investigation and rates of hospital-acquired pressure injuries reported in literature.

To account for an estimated drop-out rate of 30%, 67 subjects must be enrolled to assure, that 50 subjects will complete the investigation.

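### The 30% drop-out rate and the 67 enrolled in sections 6 and 10.2 do not agree: at 30%, 67 gives about 47 completers, and the replacement rule meant to secure 50 is not stated unambiguously

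*Combined protocol and SAP*

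**What the plan says.** Section 10.2 plans 67 enrolled with at least 50 completers and judges this size sufficient to evaluate safety. It also rests the planned precision of the exploratory endpoint (an upper 95% limit of 7.2% or less) on 50 completers. It closes with: "To account for an estimated drop-out rate of 30%, 67 subjects must be enrolled to assure, that 50 subjects will complete the investigation".

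Section 6 gives the same derivation in other words: "Considering a drop-out rate of 30%, the required total number of subjects to be enrolled in the trial shall be 67". It also defines the completers: "50 subjects are required to complete the investigation with at least 24 hours of wear time to be counted as completers". Section 6.2 requires an "expected hospital-stay of more than 24 hours from visit 1".

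On replacement, section 6.5 first says: "If dropouts are more than 17 subjects, which entails less than 50 completers, subjects shall be replaced by new subjects". Later in the same section it says: "Withdrawn subjects will not be replaced by new subjects". Section 6.4 says that once the sponsor's clinical manager knows "that 67 subjects have been enrolled, the recruitment will stop". The only exception there is for patients already informed and still deciding. Section 15.5 budgets for 67 participants.

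**The concern.** An enrolment total derived from a completer target and a drop-out rate should follow from them by one division, and here it does not. The same mismatch appears in two sections, so it is not an isolated misprint. Section 10.2 goes further and treats 67 as a guarantee.

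At stake is the minimum of 50 completers. Section 10.2 uses it for the precision of the pressure-injury proportion and, together with the 67 enrolled, as the basis for calling the study large enough to evaluate safety. If 30% is the real expectation, the plan foresees missing its own minimum unless dropouts are replaced. Whether they will be is the point on which sections 6.4 and 6.5 are unclear.

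**Working it through.** **Inputs.** Completers required: 50 (sections 6 and 10.2). Enrolled: 67 (same). Drop-out: 30% (same). Replacement threshold: more than 17 dropouts (6.5). Confidence interval: exact binomial, two-sided 95% (10.1 to 10.3). Independent drop-out between subjects is my assumption; the plan states no model.

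**1. Trying to reproduce 67.** Enrolment = completers / (1 − drop-out rate).
- At 30%: 50/0.70 = 71.43, rounded up to 72. This is not 67.
- The common mis-inflation, 50 × 1.30 = 65, is not 67 either.
- At 25%: 50/0.75 = 66.67, rounded up to 67. This matches.
- Solving back from the total: 1 − 50/67 = 25.4%. The threshold in 6.5 gives the same rate: 17/67 = 25.4%, and 67 − 17 = 50.

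The total and the threshold agree with each other. The 30% agrees with neither.

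**2. Expected completers from 67.**
- At 30%: 67 × 0.70 = 46.9, with 20.1 dropouts expected.
- At 25%: 67 × 0.75 = 50.25, with 16.75 dropouts expected.

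**3. Chance of reaching 50 from 67 without replacement.** Completers ~ Binomial(67, 1 − drop-out rate).

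| Drop-out | P(at least 50 completers) | P(more than 17 dropouts) |
|---|---|---|
| 30% | 24.7% | 75.3% |
| 25% | 59.2% | 40.8% |
| 20% | 89.2% | 10.8% |

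The chance reaches 90% only at a drop-out of about 19.8% or less. Enrolling 72 would not give assurance either: at 30% it yields at least 50 completers with probability 59.8%.

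**4. What a shortfall does to the planned precision.** With zero events, the exact two-sided 95% upper limit is 1 − 0.025^(1/n).
- n = 50: 7.11%
- n = 49: 7.25%
- n = 47: 7.55%
- n = 67: 5.36%

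If the denominator is completers (10.1: "The proportion of completed subjects answering" yes), a limit of 7.2% cannot be met with fewer than 50, even with no events. If it is the ITT population, which 10.1 also names for this endpoint, that need not follow.

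**5. Extra enrolment if dropouts above 17 are replaced until 50 complete.** The mean number beyond 67 (negative binomial) is 5.0 at 30% and 1.7 at 25%.

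**The case against.** The strongest reply is that the operational figures are coherent: 67 − 17 = 50, and supply and budget are both built on 67. On that view the 30% is a mislabelled 25% and nothing is under-sized. This may well be so. The documents do not show which figure is the slip, and the percentage is wrong for the total either way.

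A second reply is that replacement supplies the assurance, so probabilities for a fixed 67 are beside the point. This stands in part: the 24.7% and 59.2% apply only if nobody is replaced. But then the assurance comes from the replacement rule and not from the 67, and that rule is not stated clearly. A reader might infer that 6.5 flatly contradicts itself. The text does not force that, because the two sentences can be read as a default with an exception above 17 dropouts. The section does not say so, however, and 6.4 provides no route for enrolling replacements after 67.

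Third, true loss may be below 30%, since a completer needs only 24 hours of wear and the expected stay must exceed 24 hours. That is fair, but the documents give no other rate, and a lower one would still leave the stated 30% wrong.

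Three further readings go too far.
- That both sections promise 50: only 10.2 uses *assure*; section 6 simply fixes the total at 67.
- That the study must enrol 72: the documents do not establish that 30% is the correct figure.
- That a shortfall defeats the study: the exploratory comparison in 10.4 is not tied to 7.2%, 10.4 sets no formal safety criterion, and the primary and secondary endpoints use all consented subjects.

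**Conclusion.** The error stands as an internal inconsistency, stated twice: 30% drop-out, 67 enrolled and 50 completers cannot all hold. At 30% the expected shortfall is 50 − 46.9 = 3.1 completers; at 25% there is none on average. This part is plain arithmetic and needs no assumption.

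The claim of assurance in 10.2 fails at both rates unless dropouts are replaced. That part rests on independent drop-out and on enrolment stopping at 67. The replacement wording in 6.4 and 6.5 is a secondary point: it is ambiguous and not necessarily contradictory. At the plan's own 30%, though, it would be called on about three times in four.

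The consequence is limited to the 50-completer minimum, which 10.2 cites for exploratory precision and, with the 67 enrolled, for the adequacy of the safety evaluation. With zero events and a completer denominator, falling from 50 to 47 moves the upper limit from 7.11% to 7.55%. No formal test or safety analysis set changes. The point should be fixed, and the fix is cheap.

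**What to change.** **Sections 6 and 10.2.** Make the percentage and the total agree, by one of two routes that add no patients:
- State 25% drop-out with about 50 expected completers from 67, if the sponsor has grounds for that rate.
- Keep 30%, state about 47 expected completers from 67, and restate the 50 required (section 6) and the minimum of 50 (section 10.2) as a target that depends on replacement. Without that second change, the new sentence would conflict with the requirement beside it.

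**Section 10.2.** Replace *to assure* with *expected to give*.

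**Sections 6.4 and 6.5.** Reconcile the two sentences in 6.5 and the stop in 6.4 into one replacement rule, consistent with whether 50 is kept as a requirement or treated as a target.

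**If enrolment has closed.** The planned dates suggest this (last subject completed 8 December 2022, document dated 28-03-2023). In that case, report in the clinical investigation report the number of completers under the 24-hour definition, the drop-out rate, the precision achieved and which replacement sentence was followed.

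**Cost.** A few sentences, or one paragraph in the report. The downside is a less favourable stated completer count, or the need to justify 25%. Extra enrolment arises only if the existing instruction to replace is kept: on average about 5 subjects beyond 67 at 30%, or about 1.7 at 25%, against a budget for 67.

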10.3. Level of significance and power

A two-sided significance level of 5% will be applied. For a description of the power see section 10.2 above.

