10.4. Pass/fail criteria

There will be no formal success criteria for safety in this PMCF investigation.

The estimate rate (proportion) of hospital-acquired pressure injuries in hospital-admitted patients with a 95% confidence interval must be comparable to the confidence proportion and interval of the results found by Mölnlycke (5.3% [2.3%; 10.1%])³.

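### The two-sided 5% level in section 10.3 is tied to no comparison: the plan sets one 95% interval beside another and asks that they be comparable, without a rule, so the error rate depends on the reading chosen

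*Combined protocol and SAP*

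**What the plan says.** Section 10.3 states: "A two-sided significance level of 5% will be applied". It names no hypothesis and no test, and for power it refers back to section 10.2.

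Section 10.1 plans descriptive summaries of the primary and secondary endpoints. For the exploratory endpoint it plans a one-sample interval: "By use of an exact test in the Binomial distribution a 95% confidence interval will be estimated for the proportion".

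The link to the reference trial's control group, 5.3% [2.3%; 10.1%], is made in two places. Section 10.2 says "The confidence interval is then to be compared with the confidence interval of the results found by Mölnlycke". Section 10.4 sets no success criterion for safety, but requires the pressure-injury estimate "with a 95% confidence interval must be comparable to the confidence proportion and interval of the results found by Mölnlycke". Neither section says what makes two intervals comparable. The synopsis also announces comparisons with other published rates and gives no method for them.

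**The concern.** A significance level has meaning only when it belongs to a decision. The one decision in the plan is the pass/fail requirement in section 10.4, which sets two separate 95% intervals side by side. That is not a 5% comparison of two proportions. If the rule is overlap, it is far stricter than 5% before it calls a difference. Other rules that the same words allow behave quite differently.

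At stake is the interpretation of the study's only pass/fail criterion. With the rule open, the same count can be reported as comparable or not comparable, and the choice can be made once the count is known. Under overlap, an observed rate three to four times the reference rate could be reported as comparable.

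**Working it through.** **Inputs.** 50 completers (section 10.2). Up to 67 if all enrolled subjects enter the ITT set that section 10.1 assigns to this endpoint. Reference control 5.3% [2.3%; 10.1%] (sections 10.2 and 10.4). Exact binomial intervals (sections 10.1 and 10.2). The reference counts are not in the documents and are inferred in step 1.

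**Step 1: the reference interval.** Exact limits for x of n are the 0.025 quantile of Beta(x, n−x+1) and the 0.975 quantile of Beta(x+1, n−x). For 8/152 = 5.26% they are 2.30% and 10.11%, which reproduces the plan's figure. Among sizes 20 to 399 with 1 to 29 events, no other count does.

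**Step 2: the power that section 10.3 points to.** Section 10.2 says "50 completing subjects will give a power of more than 80% to show an upper 95% confidence limit of 7.2% or less", at a true rate of 1.2%. The upper limit for 0/50 is 1 − 0.025^(1/50) = 7.1%; for 1/50 it is 10.6%. Only 0/50 qualifies, so power is 0.988^50 = 54.7%, and the stated figure does not reproduce. That is a separate matter. What counts here is that it is a one-sample statement and gives no power for the comparison in section 10.4.

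**Step 3: three readings of *comparable*, n = 50.** The last two columns compare x/50 directly with 8/152.

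| x/50 | exact 95% CI | overlaps [2.3; 10.1] | contains 5.3% | estimate inside [2.3; 10.1] | Fisher p | Newcombe 95% CI for difference |
|---|---|---|---|---|---|---|
| 6 (12%) | 4.5 to 24.3 | yes | yes | no | 0.115 | −1.2 to 18.8 |
| 7 (14%) | 5.8 to 26.7 | yes | no | no | 0.059 | 0.2 to 21.2 |
| 8 (16%) | 7.2 to 29.1 | yes | no | no | 0.029 | 1.7 to 23.5 |
| 9 (18%) | 8.6 to 31.4 | yes | no | no | 0.015 | 3.2 to 25.8 |
| 10 (20%) | 10.03 to 33.7 | yes | no | no | 0.003 | 4.8 to 28.0 |
| 11 (22%) | 11.5 to 36.0 | no | no | no | 0.001 | 6.3 to 30.2 |

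Overlap and Fisher at 5% disagree for 8 to 10 of 50. Uncorrected chi-square (p = 0.041 at 7/50) and the Newcombe interval widen the band to 7 to 10.

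**Step 4: chance of calling a difference when both true rates are 5.3%.**
- Overlap: sum Bin(x; 50, p) × Bin(y; 152, p) over all pairs with disjoint exact intervals. Result 0.12% (study higher) + 0.01% (study lower) = 0.13%. At common rates of 3% and 8% it is 0.06% and 0.24%.
- Interval must contain 5.3%, held fixed: P(X ≥ 7) = 1.6%. It can never flag a low rate, because even 0/50 has an upper limit of 7.1%. If y/152 is treated as random, the same double sum over pairs where the study interval excludes y/152 gives 5.3%. It gives 8.0%, 4.2% and 6.6% at common rates of 1.2%, 3% and 20%.
- Estimate must lie inside [2.3%; 10.1%], held fixed: P(X ≤ 1) + P(X ≥ 6) = 25.0% + 4.8% = 29.7% (from unrounded terms 0.2495 + 0.0479). This reading also fails 0/50 and 1/50, which together have probability 87.9% at the planned rate of 1.2%.
- For comparison, by the same double sum, Fisher at 5% gives 3.1% and the Newcombe interval 3.7%.

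**Step 5: chance of flagging a true excess, reference held at 8/152.** At true rates of 15% and 20%: overlap, P(X ≥ 11) = 12% and 42%; Fisher, P(X ≥ 8) = 48% and 81%; interval containing 5.3%, or Newcombe, P(X ≥ 7) = 64% and 90%; estimate inside the range, P(X ≥ 6) = 78% and 95%.

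**Step 6: 67 analysed.** Overlap fails from 13/67 (lower limit 10.8%), Fisher from 10/67 (p = 0.029). The band of disagreement moves to 10 to 12.

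**The case against.** The strongest reply is that the plan never mentions overlap. A reader might infer that the comparison does run at about 0.1%, or that 8 to 10 of 50 would certainly be reported as not different. The documents do not support either inference. Section 10.4 names the reference proportion as well as its interval, and the two other readings in step 3 flag an excess sooner than Fisher's test does. The 0.13% and the 8 to 10 band belong to the overlap reading alone.

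It can also be said that a 5% level is the ordinary counterpart of the one-sample 95% interval in section 10.1, so nothing is contradicted. That is fair for estimation. The interval-containing-5.3% reading even averages near 5% in one framing, but this arises because the conservatism of the exact interval happens to offset the ignored sampling error of the reference, and the figure moves between 4.2% and 8.0% over the rates tried. Nothing in the plan selects that reading.

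A reader might further infer that a safety signal would be missed. Section 5.5 assigns this endpoint to performance. Local pressure injury is an anticipated adverse device effect in Table 6, section 18.7 requires device effects to be reported within 24 hours, and section 19 provides for suspension on suspicion of unacceptable risk. A raised count would come to light by those routes.

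Finally, the endpoint is exploratory and the control is external, from a trial in trauma and critically ill patients. That limits the weight of any comparison. It does not excuse an undefined rule in the plan's only pass/fail criterion, particularly as section 10.2 judges the sample large enough for comparative conclusions.

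**Conclusion.** The point stands in conditional form. The 5% level in section 10.3 is tied to no comparison, and the interval-against-interval comparison in sections 10.2 and 10.4 has no rule. Depending on the reading, an excess is first flagged at 6, 7 or 11 of 50. The chance of calling a difference at a common rate of 5.3% ranges from about 0.13% (overlap) to about 30% (estimate inside the reference range, with the reference held fixed). Under overlap, 8 to 10 of 50 would pass despite Fisher p of 0.029 to 0.003.

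These figures assume 50 analysed subjects, inferred reference counts of 8/152, and the framing stated for each (reference random or fixed). With the reference interval fixed, the overlap rate falls to about 0.005%. The weight is moderate: this should be corrected, but it does not touch the primary or secondary endpoint.

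**What to change.** In sections 10.2 and 10.4, replace the interval-against-interval comparison with the 95% confidence interval for the difference in proportions, for example Newcombe's, computed from this study's counts and the reference trial's published counts. The inferred 8/152 must be checked against that publication. Then state that:

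- the two-sided 5% level in section 10.3 refers to this interval;
- an interval that includes zero, or two separate intervals that overlap, will not by itself be read as evidence of comparability (even 0/50 gives −10.0 to 2.3 percentage points);
- the result is exploratory and rests on a non-randomised external control.

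If the sponsor wants to conclude comparability, a justified margin on the difference scale has to be written down as well, because the difference interval alone does not define it.

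The cost is a few sentences and one calculation, with no change to sample size, visits or data collection. The downside is an external-control comparison that must carry its caveat. If the sponsor prefers description only, delete the significance level from section 10.3 and state that overlap is not evidence of no difference.
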